10.3.1 Serious Adverse Event

A serious adverse event (SAE) is an adverse event that has:

1. Led to death,
2. Led to serious deterioration in the health of the subject, that either resulted in:
 - a life-threatening illness or injury, or
 - a permanent impairment of a body structure, or
 - in-patient or prolonged hospitalization, or
 - medical or surgical intervention to prevent life-threatening illness or injury or permanent impairment to a body structure or a body function,
3. Led to fetal distress, fetal death or a congenital abnormality or birth defect.

Note: Planned hospitalization for a pre-existing condition, or a procedure required by the study, without serious health deterioration is not considered a SAE.

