If the nodule is fully removed in crossover cases, then the primary endpoint is met. The nodule may be removed per the surgeon's judgement. The pathology findings will then identify the entire case as either benign or malignant, and the primary endpoint is met.

If Diagnosis is Non-malignant

If the nodule is deemed non-malignant, cells are identifiable, then the positive box for diagnosis is checked, and:

- The nodule must have an intact margin of a cell as a perimeter to be diagnostic.
- The type of nodule (ground glass opacity, etc.) is collected from the pathology report.

The pathology findings will then identify the case as either benign or malignant.

9.3 Safety Objective:

Record Safety Events During Intraoperative Percutaneous Localization Only

To collect and evaluate the safety of nodule localization, including incidence and severity of localization-procedure related adverse events (AEs) and serious adverse events (SAEs) that occur during the localization procedure.

Baseline/Enrollment

All patients will be provided with information about the registry and will sign the informed consent form before any registry-related assessments are made. The following data will be collected at baseline for all enrolled patients:

- To be collected at baseline visit: Review of inclusion/exclusion criteria.

Localization Period

- The localization period begins when the needle touches the subject's skin.
- Localization ends when the localization needle is withdrawn from the subject for the final time.
- Any adverse events that develop during the localization procedure will be reported.
- Bronchoscopy-related events that occur during the alignment of the CT with the patient ("registration") will be recorded.
- Percutaneous localization step, injection of dye, injection of any microcoils, etc.

The process used for AE reporting conforms to Veran Medical Technologies, Inc., standard operating procedures (SOPs) for Medical Device Reporting (MDR)(Appendix C). Training on AE/SAE/MDR reporting practices will be provided to each participating site.

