10.2 Safety Reporting

All SAEs and device deficiencies related to the Veran system or its instruments are also to be reported directly to Veran as follows: (please send to **vSupport**, and Cc: the **PLOTS** email)

Email: [contact]

Email: [contact]

For any FDA-reportable event, please also forward to the following for awareness:

Contact: [name]
[contact]
Email: [contact]

Safety events from the localization procedure only will be collected in the registry (please refer to Appendix B for all data elements collected in Registry).

This study is being conducted under 21 CFR part 50¹ (<https://www.ecfr.gov/cgi-bin/textidx?SID=244dabc113521b0a851a5db147554fdd&mc=true&node=pt21.1.50&rgn=div5>) using a 510(k)-cleared device system. The exemption in 21 CFR 812.2(c)(2) applies to this study, where the device is substantially equivalent to its predicate, and the device is being used in accordance with its labeling.

Study sites are likewise responsible to report adverse events and complications to their IRBs according to institutional requirements.

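### The SAE definition in section 10.3.1 counts intervention to prevent permanent functional impairment, but its permanent-impairment bullet names body structure only

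*Combined protocol and SAP*

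**What the plan says.** Section 10.3.1 defines an SAE as an adverse event that led to death, to a serious deterioration in health, or to fetal distress, fetal death or a congenital defect. The deterioration item opens with "Led to serious deterioration in the health of the subject, that either resulted in" and is followed by four results:

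1. "a life-threatening illness or injury, or"
2. "a permanent impairment of a body structure, or"
3. "in-patient or prolonged hospitalization, or"
4. "medical or surgical intervention to prevent life-threatening illness or injury or permanent impairment to a body structure or a body function"

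A note excludes planned hospitalization for a pre-existing condition, or a procedure the study requires, where there is no serious deterioration.

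The classification is used in three places:

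- The safety objective in section 9.3 covers safety "including incidence and severity of localization-procedure related adverse events (AEs) and serious adverse events (SAEs").
- Section 11.2.1 has SAEs and AEs listed and summarized.
- Section 10.2 states: "All SAEs and device deficiencies related to the Veran system or its instruments are also to be reported directly to Veran". Sections 10 and 10.3 direct investigators to form 3500A for relevant SAEs and for device complaints.

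**The concern.** Bullets 2 and 4 describe the same harm at two stages: the impairment that occurs, and the impairment that intervention heads off. One would expect them to share a scope. Instead bullet 4 covers structure and function, and bullet 2 covers structure alone. The milder course, where function is rescued, is an SAE by rule. The worse course, where function is permanently lost, is an SAE only if it also meets some other criterion.

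The documents give no reason for the difference, and bullet 4 shows that function was considered relevant to seriousness. At stake is whether a lasting functional injury carries the SAE label, and with it a place in the SAE summary and the SAE-specific report to the sponsor. Section 3 describes the subjects as typically older, with comorbid lung disease and poor lung function before surgery, so loss of function is a relevant kind of harm here.

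**Working it through.** The plan states no figure on this point, so the check is a reading of the text in three steps.

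**Step 1. Is the list closed?** The stem admits a deterioration only through one of the listed results. There is no residual clause for other medically important events. A functional impairment must therefore match a listed criterion to be serious.

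**Step 2. Does another section supply the missing term?**

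- Sections 10 and 10.3 refer to a device-related serious injury but do not define it.
- Section 10.4 covers causality only.
- Section 10.5 records the outcome as resolved or continuing and does not identify permanent impairment.
- Section 10.6 grades the severity of hemorrhage only.

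Within the text available, section 10.3.1 is the only definition of seriousness.

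**Step 3. Apply the list to two events.** Assume that both are serious deteriorations in the sense of the stem.

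*Event A:* permanent functional impairment is threatened, and an intervention prevents it. Bullet 4 is met, so A is an SAE.

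*Event B:* permanent functional impairment occurs, with no intervention to prevent it.

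| Criterion | Is B captured? |
|---|---|
| Death | No |
| Life-threatening illness or injury | Only if B was also life-threatening |
| Permanent impairment of a structure | Only if a structural injury is identified |
| In-patient or prolonged hospitalization | Only if the stay is prolonged |
| Intervention to prevent impairment | No, because there was none |
| Fetal harm or birth defect | No |

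The hospitalization row gives limited protection. Every subject is already admitted for resection, generally for 2 to 5 days according to the synopsis, and the note sets planned admission aside. For an event during this admission, only a longer stay would count.

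If B has none of the qualifying features in the table, it meets no criterion and is classed as a non-serious AE, while A is an SAE.

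**What then happens to B in the plan?** It is still recorded, listed and summarized as an AE under section 11.2.1. It does not enter the SAE summary, and the SAE part of the section 10.2 reporting rule does not apply to it.

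**The case against.** The strongest reply is that little is lost.

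- **The event stays in the safety data.** It is listed as an AE, with causality and outcome recorded under sections 10.4 and 10.5. The synopsis safety objective is the incidence of device-related adverse events, where seriousness plays no part.
- **Other reporting duties remain.** Sections 10 and 10.3 require user facilities to report a device-related serious injury to the manufacturer. Section 10.2 sends related device deficiencies to the sponsor whatever the seriousness. Sections 9 and 10.2 require reporting of adverse events and complications to IRBs.
- **Few events would fall in the gap.** Section 8.2.3 names bleeding and pneumothorax as the localization risks. Many lasting functional injuries would qualify through another bullet.
- **Permanence is hard to judge.** Section 10.3 collects localization events through discharge, so the corrected bullet might seldom be applied with confidence.

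All four stand as limits on weight. None removes the inconsistency. An AE listing does not replace the SAE label that section 9.3 asks for. Serious injury is undefined in the text, so it cannot be shown to cover the same cases. Doubt about permanence applies equally to the structural criterion already there.

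A reader might infer more: that the wording removes a class of severe harms from the safety results and from reporting. The documents do not support that, for the first two reasons above. Nor is a lasting nerve deficit a clean example, since a nerve is itself a body structure and bullet 2 may already cover it.

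A reader might also attach a rate. One event is 1/70 = 1.4% or 1/100 = 1.0% of the 70 to 100 evaluable subjects in section 11.1. With no SAE recorded, the exact two-sided 95% upper limit, 1 − 0.025^(1/n), is 5.1% at n = 70 and 3.6% at n = 100. These figures hold for any single misclassified event and say nothing about how often this gap would operate. The documents give no frequency for such events and do not specify a confidence interval for SAE incidence.

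**Conclusion.** The inconsistency is real and lies between two bullets of the same list. The consequence is narrow: a permanent, purely functional injury that meets no other criterion is labelled a non-serious AE, and so is missing from the SAE summary and from SAE-specific reporting to the sponsor.

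The effect is small and cannot be expressed as a rate shift from these documents. No hypothesis or sample size depends on the SAE count. The point is worth correcting because section 10.3.1 decides which harms count as serious and the correction is very cheap.

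The conclusion assumes that sites apply the definition literally and that the Appendix C forms, whose content is not in the text reviewed, do not supply a wider definition of seriousness for the registry.

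**What to change.** Extend the permanent-impairment bullet in section 10.3.1 to name body function alongside body structure, using the scope already present in the intervention bullet. Update the site training on AE and SAE reporting to match.

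Re-check AEs already recorded as non-serious against the aligned definition, starting with those whose outcome under section 10.5 is continuing. Where permanence was not known at discharge, note that in the record so that the classification can be understood later.

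The cost is one phrase in the protocol through the usual amendment route, a training update and a short review of existing AE records. The downside is that the SAE count may rise slightly.

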10.4 Causality – Adverse Event Relationship

The PI will assess the relationship of an adverse event to the device and procedure as follows:

- *Not Related*: No relationship appears to exist between the AE and the device and/or procedure.
- *Related*: The AE follows a plausible temporal sequence following administration of the study device and/or execution of the procedure.
- *Undetermined*: It is not possible to determine the relationship of the AE with the study device and/or procedure.

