OBJECTIVES	
The registry is aimed developing a high-quality set of data regarding intraoperative percutaneous localization of peripheral pulmonary nodules (PPNs), and then identifying and promulgating efficient, evidence-based best practices for this technique. The resection procedure itself is standard of care and follows the investigator's standard protocol.
 
Successful localization of PPNs is a challenge involving multiple factors, beginning with the subjects' health, lung function and also factors specific to the nodule including location within the lung, size, distance from the lung surface, whether solid or ground glass and proximity to a fissure. Hard to see or palpate nodules are currently localized with dye and/or hook wires or fiducials, either endoscopically or percutaneously. Successful, large, prospective studies have not been reported using modern electro-magnetic navigation (EMN)-guided percutaneous intraoperative localization, and different techniques (dye vs. fiducial vs. hook wire etc.) have not been evaluated. It is for these reasons that the different localization techniques used with EMN-guided percutaneous localization will be collected for patients having a suspicious nodule and who undergo percutaneous intra-operative localization and immediate resection.
 
This registry aims to record the localization techniques used by thoracic surgeons and IP/surgical teams to identify PPNs using the SPiN Thoracic Navigation System™ in the hands of trained physicians. The objectives of this study will be to accomplish the

	primary and secondary objectives listed below, and to observe localization in a real-world context of pulmonary resection.
PRIMARY OBJECTIVE	Successful percutaneous localization of PPN. This is defined as the percentage of subjects in whom the nodule is successfully localized and removed in the first resected specimen. A pathological specimen with clear margins will count as a successful localization.
SAFETY OBJECTIVES	
1. Report the incidence of device-related adverse events that occur during the localization procedure.

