	
The study will enroll between 70 and 100 subjects who fall within current clinical practices to have their PPNs removed at approximately 5 geographically diverse sites across the US. These subjects will undergo intraoperative, EMN-aided percutaneous nodule localization and subsequent resection as part of their normal care. Safety data (adverse and severe adverse events) regarding these subjects will be collected for the localization procedure.
 
All surgical and post-surgical treatment decisions and clinical assessments will be at the discretion of the subject's thoracic surgeon. Eligible subjects from participating sites will be enrolled following identification of a qualifying nodule, and meeting inclusion/exclusion criteria and completing informed consent.
 
Data Collection
 
Registry data will be collected before, during, and after the procedure from the subject's medical records by site personnel. Based on current clinical practice, it is anticipated that subjects will be seen following nodule identification and workup to determine the treatment plan and preparation for surgery (baseline visit). The size and location of the nodule, demographic data and data about smoking history will be collected. Comorbidities will be collected from medical history, and the subject's lung function test results collected.
 
The subject will return to the site for surgery. A non-contrast chest CT scan is recommended within 24 hours/same day as surgery, as a clinically indicated procedural planning tool (Appendix D – Veran CT scan). Otherwise, a non-contrast chest CT scan within the past 15 days is adequate. Subjects are typically given general anesthesia for surgery. The localization technique and material used will be recorded, including volume and type of dye, which needle used, and any other fiducial markers (e.g. microcoil). Localization procedure-related adverse events and device-related adverse events will be recorded. The type and technique of resection performed will be collected (VATS, RATS, thoracotomy, etc.). Subjects recover in hospital and are discharged per standard of care. Any localization-related adverse events will be reported, however the overall lung surgery procedure itself is not being studied (approved indication). Subjects will typically return to the clinic a few times to be seen for scheduled post-operative visits to monitor recovery.
 
A secure, site portal that is 21 CFR part 11 compliant is used for the electronic data entry and reporting at each site, which includes appropriate firewalls between sites and users to protect subject

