4. OBJECTIVES

The registry is aimed at developing a high-quality set of data regarding the percutaneous localization of PPNs. The localization registry itself is nested within the subjects' lung resection operation. Analyzing and promulgating evidence-based best practices for lung nodule localization will allow surgeons to identify technical solutions and reproducible methods.

This registry will record procedural data for trained thoracic surgeons using the SPiN Thoracic Navigation System™ and tools. Diagnostic yield will measure successful localization of the lesion in the resected specimen. Localization-related safety events will be collected.

4.1 Primary Objective:

Successful percutaneous localization of PPN.

To evaluate the accuracy of percutaneous nodule localization using the SPiN Thoracic Navigation System™ and its accessories, Veran will record the percentage of successful resections that result in the complete removal of the patient's nodule, with a negative margin. The diagnostic yield is calculated as the percentage of patients who have intra-operative localizations resulting in complete removal of nodule, divided by the total number of evaluable subjects. Evaluable subjects are those who complete the localization procedure.

Primary Objective: Successful percutaneous localization of PPN.

This is defined as the percentage of subjects in whom the nodule is successfully localized and removed in the first resected specimen. A pathological specimen with clear margins will count as a successful localization.

4.2 Safety Objective:

Collect safety data for localization procedure.

4.3 Secondary Objectives:

Secondary Objectives: Use as per synopsis – including margin.

- 4.3.1 Report localization methods and techniques – dye and materials used, volume of dye (methylene blue, ICG etc.), other materials such as microcoils, hook wires etc. Details regarding these techniques will be collected.
- 4.3.2 Collect data on intraoperative percutaneous localization time and duration of total surgical procedure.
- 4.3.3 Record nodule characteristics, including location in the lobe, distance from pleura, distance from surface of skin to target, morphological appearance, solid vs. ground glass etc.
- 4.3.4 Record weight of excised tissue and margin.
- 4.3.5 Report type of surgical resection performed (segmentectomy or wedge) and resection technique (VATS, RATS, thoracotomy).

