10.3 Adverse Events – Data Collection for Localization Events

An adverse event (AE) is any untoward medical occurrence, unintended disease or injury, or untoward clinical signs (including abnormal laboratory findings) in subjects, users or other persons, whether or not related to the investigational medical device. Note: Pre-existing conditions are not considered to be adverse events unless there is a change in the nature or severity of the condition.

We will collect data on the localization adverse event through subject discharge from hospital. Principal Investigators were taught to use FDA 3500A MedWatch (Appendix C) and were taught to fill those out during the investigator meeting, for relevant SAEs and also for medical device complaints. This registry's primary safety objective is to collect localization-related safety events in patients undergoing localization prior to wedgeectomy.

The Medical Device Reporting (MDR) regulation (21 CFR 803) contains mandatory requirements for device user facilities (including hospitals, surgical facilities and other) to report certain device-related serious adverse events and product problems to the FDA. These are described in the forms in Appendix C, and the FDA's Guidance for User Facilities.

- User facilities must report a suspected medical device-related death to both the FDA and the manufacturer within 10 days.
- User facilities must also report a medical device-related serious injury to the manufacturer (Veran Medical Technologies, address below).
- In addition, each IRB and institution may have its own policies regarding the content, format, and timing for the reporting of safety information.

¹ The Electronic Code of Federal Regulations (www.ecfr.gov) - <https://www.ecfr.gov/cgi-bin/textidx?SID=244dabc113521b0a851a5db147554fdd&mc=true&node=pt21.1.50&rgn=div5> accessed 4/16/2019.

Each investigator or delegate is responsible for fulfilling these duties.
Please report device serious adverse events to Veran as noted below on form 3500A
(Appendix C).

Please scan and send completed forms to:
Email: [contact]
Email: [contact]

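### Section 10.4 defines relatedness jointly for device and procedure and on timing, so it does not ensure that device-related adverse event incidence can be derived

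*Combined protocol and SAP*

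**What the plan says.** The synopsis, under Safety Objectives, lists one item: "Report the incidence of device-related adverse events that occur during the localization procedure". Under Data Collection it names two kinds of event: "Localization procedure-related adverse events and device-related adverse events will be recorded".

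Section 10.4 is the only rule for assigning cause. Its lead-in is "The PI will assess the relationship of an adverse event to the device and procedure as follows", followed by three levels. *Not Related* is "No relationship appears to exist between the AE and the device and/or procedure". *Related* is "The AE follows a plausible temporal sequence following administration of the study device and/or execution of the procedure". *Undetermined* applies when the relationship cannot be determined. All three levels join device and procedure with and/or.

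Elsewhere the safety objective is worded differently. Section 4.2 has "Collect safety data for localization procedure". The safety objective in section 9.3 speaks of events related to the localization procedure. Section 10.3 says "This registry's primary safety objective is to collect localization-related safety events in patients undergoing localization prior to wedgeectomy", and the opening of section 10 is close to that.

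**The concern.** The synopsis promises a device-specific incidence. The causality rule does not require a device-specific rating.

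Timing separates causes poorly in this setting. General anesthesia, registration bronchoscopy, needle puncture and resection follow one another in a single session (sections 9.8 and 9.9). The localization risks named in section 8.2.3, bleeding and pneumothorax, could come from more than one of these steps.

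At stake is the numerator of the registry's headline safety result. If only a joint rating is available, a count of events related to device or procedure could be published as device-related incidence. Attribution is also better made at the time than rebuilt later from charts.

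**Working it through.** The plan states no expected device-related rate and no sample size calculation (section 11.1), so there is no figure to reproduce. The check sets the texts side by side and asks what each rating allows one to count.

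**1. What a joint rating identifies.** Among N evaluable patients, let d be those with a device-related event, p those with a localization-procedure-related event, and b those with both. A joint rating counts r = d + p − b. The synopsis objective is d/N. One observed count does not determine three unknowns. It gives only d ≤ r. Separate ratings give d, p and b directly.

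**2. Whether two ratings alone would be enough.** Not under the present definition of *Related*. The localization needles are themselves study devices (section 6.1), so use of the device and execution of the procedure largely coincide in time. An event during needle placement would satisfy the timing test for both.

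**3. Whether the levels exclude one another.** As worded, they need not. Take an event during localization that the PI attributes to anesthesia. It has a plausible temporal sequence, which meets *Related*. The PI also sees no relationship, which meets *Not Related*. Two sites could classify it differently.

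**4. Which procedure is meant.** Section 10.4 does not say. Section 9.3 runs the localization period from first skin contact of the needle to its final withdrawal, yet also records bronchoscopy events during registration, which comes before the needle (section 9.9). Section 9 collects events from the start of localization to the start of wedge resection. Section 10.3 collects data on the localization event through discharge.

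**5. Whether another route supplies the figure.** Section 10.2 sends SAEs and device deficiencies related to the system directly to the sponsor. Sections 10 and 10.3 ask for device SAEs on form 3500A, and section 10.1 asks for deficiencies on that form. A non-serious device-related event that involves no deficiency falls outside this route. A minor bleed that does not meet the SAE definition in section 10.3.1 is an example.

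**6. Sensitivity to attribution.** N is 70 to 100 (section 11.1). Moving one patient into or out of d changes d/N by 1/N: 1/70 = 1.4 percentage points, 1/100 = 1.0 percentage point.

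**The case against.** A reader might infer that each event is rated only once. The documents do not say so. The lead-in to section 10.4 names device and procedure, one set of definitions could be applied to each in turn, and the synopsis names the two kinds of event separately. The adverse event form is not in the documents, and section 11.2.1 leaves the analysis to a separate SAP. Two fields may exist. What stands is that section 10.4 does not require them, and that a definition resting on timing would not separate the two even if they did.

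A reader might also say that causality rests on timing alone throughout. That is true of *Related* only. The other two levels call for judgement, so a PI can rate a well-timed event otherwise.

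Sections 4.2, 9.3, 10 and 10.3 state a localization-related objective, which a joint rating could largely serve if the procedure means localization. That is fair, but the synopsis objective is still in force, so the two need to be aligned.

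The collection windows in sections 9 and 9.3 put events first arising during resection largely outside the count. This stands. It narrows the confusion mainly to device, localization, registration bronchoscopy and anesthesia.

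Finally, this is a descriptive registry with no hypothesis. That limits the consequences, but a descriptive incidence still needs a defined numerator.

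**Conclusion.** The point holds in a limited form. As written, section 10.4 does not ensure that the device-related incidence promised in the synopsis can be derived. To say that it cannot be obtained would go too far: the unseen form may hold separate fields, and serious device-related events and deficiencies have their own route. The gap that remains is mainly the non-serious device-related events.

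The documents do not allow an overall size to be given. A reader might take the five pneumothoraces in 24 patients (21%) from the pilot study cited in section 7 and conclude that device-related incidence lies anywhere from 0% to 21%. That range says only that a subset lies between none and all, and the pilot concerned biopsy rather than localization before resection. The figure that can be supported is 1.0 to 1.4 percentage points for each patient with unresolved attribution, assuming 70 to 100 evaluable patients as the denominator.

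**What to change.** In section 10.4, require the PI to rate each adverse event twice, each time as *Not Related*, *Related* or *Undetermined*:

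1. against the SPiN system and its tools, including the localization needles;
2. against the localization procedure, stated to include registration bronchoscopy.

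Base *Related* on more than timing, so that an event clearly explained by another cause, such as anesthesia, is not counted as device-related. Report device-related and localization-procedure-related incidence separately, with *Undetermined* shown on its own. Align the safety objective across the synopsis and sections 4.2, 9.3, 10 and 10.3. A separate rating for anesthesia or resection is not needed, because the synopsis says that the surgery itself is not being studied.

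The cost is a wording change, one or two fields on the adverse event form if they are not already there, and a PI judgement that will be uncertain for some events. Patient care does not change.
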